7.6. Changes to Planned Analyses

The changes in planned analyses between the protocol and SAP are the following:

- The protocol indicates that an optional interim analysis may be conducted for efficacy. This SAP confirms that an interim analysis was not performed.
- Section 9.3 of the protocol states “up to” 140 subjects will be enrolled” and is inconsistent with section 4, which states “approximately 140 subjects will be enrolled”. The SAP has been modified to clarify that “approximately” 140 subjects will be enrolled. -
- The protocol was not amended to describe study conduct changes due to COVID-19. This SAP summarizes changes in study conduct due to COVID-19 restrictions, as well as the additional analyses for efficacy, safety and protocol deviations.

8. STUDY POPULATION SUMMARIES

8.1. Enrollment

The total number and percentage of subjects for each Analysis Set defined in section 6 will be summarized among the ENR by baseline medication group and RND by randomized treatment group. For the ENR and RND, the number of subjects who enrolled by country and study site/Investigator will be summarized.

8.2. Subject Disposition

All subjects who provide informed consent will be accounted for in this study. The number and percentages of screen failure subjects will be presented by overall among the SCR. For each period, the number and percentages of subjects who entered, received at least one dose, completed, are still ongoing and withdrew from each period, including reasons for withdrawal, will be presented overall and by Baseline Medication Group based on the ENR.

The number and percentages of subjects who received at least one dose, completed, are still ongoing and withdrew from the DBRW, including reasons for withdrawal, will be presented overall and by randomized treatment group based on the RND.

Note that the subject disposition listing will capture the reason for withdrawal including any subject who discontinues from the study due to acquiring COVID-19 or due to COVID-19 restrictions.

8.3. Demographic and Baseline Characteristics

Demographic and other baseline characteristics data will be summarized using descriptive statistics for the SAF, mITT, and PK. Additionally the data will be summarized by the subgroups of stable dose regimen for DBRW SAF, and Idiopathic Hypersomnia diagnosis (long sleep vs without long sleep) for SAF.

Demographic and other baseline characteristics include:

- The age entered by the sites will be used. If it is missing, then it will be derived from date of birth and informed consent date. For countries where regulations allow only the year of birth to be entered for birth date, July 1st of that year will be used for the calculation of age.
- Gender
- Race - subjects who reported more than one race will be reported under 'multiple' race category
- Ethnicity
- Height (cm), Weight (kg), BMI (kg/m²)
- Childbearing potential
- Country

- CGIs severity at baseline
- ESS at baseline
- IHSS at baseline
- Baseline Medication Group

8.4. Medical/Surgical History

Surgical and medical history will be coded using the Medical Dictionary for Regulatory Activities (MedDRA) dictionary, version 19.1, and are defined as those medical conditions/diseases which started prior to or on the date of initial ICF signing.

The following summaries will be provided for the surgical and medical history data based on the SAF and mITT.

- Past surgeries and medical conditions/diseases, other than idiopathic hypersomnia by System Organ Class (SOC) and Preferred Term (PT)

If a subject reports a past medical condition/disease, surgery or past medication more than once within a SOC or PT, the medical condition/disease, surgery or past medication will be reported only once for that SOC or PT.

Disease history will be summarized for the SAF and mITT. Disease history variables include:

- Time since IH symptom onset and initial diagnosis (years) - calculated relative to date of the signature of the ICF (See Appendix 2 for handling partial dates)
- ESS Score at diagnosis
- Diagnosis by ICSD-2 or ICSD-3
- Idiopathic Hypersomnia diagnosis (Long sleep vs without long sleep)
- Symptoms of idiopathic hypersomnia at the time of diagnosis

8.5. Prior and Concomitant Medications

Medications will be coded to the anatomical therapeutic class (ATC) level 4 and preferred drug name using the World Health Organization (WHO) drug dictionary, version 01Sep2018, and will be classified as follows:

- **Past medications** are defined as any medications which started prior to the first dose of OL study drug in the OTTP.
- **Concomitant medications** will be defined as any medications started prior to, on or after the first dose of OL study drug up to the last dose of study drug and continued during the study treatment. Concomitant medications will be also defined for each study period as follows:

- **For the OTTP**, concomitant medications are defined as any medications that ended on or after the first dose of OL study drug in the OTTP and started prior to, on or after the first dose of OL study drug in this study period up to
 - the end of this study period for subjects who entered the SDP
 - the last dose of OL study drug in the OTTP for subjects who discontinued early in the OTTP;
- **For the SDP**, concomitant medications are defined as any medications that ended on or after the first dose of OL study drug in the SDP and started prior to, on or after the first dose of OL study drug in this study period up to
 - the end of this study period for subjects who entered the DBRW
 - the last dose of OL study drug in the SDP for subjects who discontinued early in the SDP;
- **For the DBRW**, concomitant medications are defined as any medications that ended on or after the first dose of DB study drug in the DBRW and started prior to, on or after the first dose of DB study drug up to
 - the end of this study period for subjects who entered the OLE
 - the last dose of DB study drug in the DBRW for subjects who discontinued early in the DBRW;
- **For the OLE** concomitant medications are defined as any medications that ended on or after the first dose of OL study drug in the OLE and started prior to, on or after the first dose of OL study drug in this study period up to the last dose of OL study drug in the OLE;
- **Post medications** are defined as any medications that started after the last dose of study drug during the OTTP, SDP, DBRW or OLE (whichever is the latest).

Medications that span across periods will be counted as concomitant medications for each of the periods where the definition is met.

See Appendix 2 for handling of partial dates for medications.

In addition, the number of subjects for the following Xyrem dosing information at study entry groups will be:

- Unequal Nighttime Xyrem Dosages
- Equal Nighttime Xyrem Dosages
- Once Nightly Xyrem
- Twice Nightly Xyrem
- Thrice Nightly Xyrem

Medications will be summarized by ATC level 4 and preferred drug name. Additionally, disease-related medications will also be summarized and defined as those medications taken for the

treatment of idiopathic hypersomnia symptoms as indicated on the Concomitant Medication CRF.

Summaries will include all prior medication, disease related prior medications, disease related concomitant medications across the entire study, and all concomitant medications across the entire study using the SAF.

Disease Related and Concomitant Medications taken during the SDP and DBRW will be summarized overall and by randomized treatment group using the mITT.

8.6. Protocol Deviations

Protocol deviations as classified in the CTMS (type of deviation and severity) will be summarized by Baseline Medication Group and overall across all study periods using ENR.

All protocol deviations will also be provided in a listing.

Changes to study conduct due to COVID-19 restrictions will be reported as protocol deviations. These deviations will be summarized separately by the classification type in CTMS and included in a listing.

9. EFFICACY

Unless otherwise described, efficacy data will be primarily presented by randomized treatment group using mITT, and treatment comparison will be between the randomized treatment groups, JZP-258 and placebo.

9.1. Primary Efficacy Endpoint and Derivation

The primary endpoint is the change in ESS score from the end of the SDP to the end of the DBRW.

The ESS is a self-administered questionnaire with 8 questions asking the subjects how likely they would be to doze off or fall asleep in different situations (Johns 1991, Johns 2000, Broderick et al 2013). Responses range from 0 = would never doze to 3= high chance of dozing. Subjects will be asked to complete the ESS with regard to the level of sleepiness they experienced over the past week multiple times during the study. The primary efficacy analysis will utilize those assessments at the end of the SDP and at the end of the DBRW.

The ESS total score is the sum of the 8 item-scores and can range between 0 and 24. Higher scores indicate greater daytime sleepiness. If three or more item scores are missing at a specific time point, the ESS total score will be set to missing. If one or two ESS item scores are missing at a specific time point, the mean of the remaining seven or six non-missing ESS item scores at that time point will be used to impute the missing ESS item value. The ESS total score will be then calculated as the sum of the observed and imputed item scores.

9.1.1. Primary Endpoint Analysis

For the main analysis of the primary efficacy endpoint, an analysis of covariance (ANCOVA)

will be performed using the PROC MIXED SAS procedure. The model will include the change in ESS from the end of the SDP to the end of the DBRW as the dependent variable; the treatment group and baseline medication group as fixed effects as well as the ESS score at the end of SDP as a covariate. If the ESS total score at the SDP and/or DBRW is still missing after the imputation of ESS item value as specified above, the subject will be excluded from the primary analysis.

All group comparisons from the ANCOVA model will be based on Type III sum of squares. Least square mean (LS mean) and standard error (SE) will be provided for each treatment group. The difference between these two LS means along with the SE of the difference, 95% confidence interval (CI) and associated p-value corresponding to testing the hypothesis of no difference between the treatment groups will also be provided.

The normality assumption of the ANCOVA model will be examined by residual analysis using the Shapiro- Wilk test at a 0.05 significance level. If the normality assumption is considered violated, a non-parametric ANCOVA with the covariate and response variables replaced by their ranks (Conover and Iman 1982) will be used for the primary efficacy analysis of the primary efficacy endpoint. In the event of ties in the baseline or change from baseline, average ranks will be used. The ranks will be used in the ANCOVA with the rank for the change from baseline as the dependent variable, treatment and baseline medication group as fixed effects, and the rank for ESS score at the end of SDP as a covariate. P-values will be presented from the rank based ANCOVA. The estimated median difference between the change in ESS between the two treatment groups and asymptotic 95% confidence intervals will be presented using the Hodges- Lehman estimator (Hodges and Lehman 1962).

A box plot of the change in ESS from the end of the SDP to the end of DBRW by randomized treatment group will be presented.

Example SAS Code for the ANCOVA model is shown below.

PROC MIXED DATA =ANAL METHOD =TYPE3;

CLASS TRT03PN BMED;

MODEL CHG = TRT03PN BASE BMED/ RESIDUAL OUTP=RESIDUAL;

LSMEANS TRT03PN/DIFF CL;

RUN;

The SAS code below evaluates the assumption of normality for the residuals from the above ANCOVA model using the Shapiro Wilk test.

PROC UNIVARIATE DATA=RESIDUAL NORMAL;

VAR RESID;

RUN;

If normality assumption is violated ($P<0.05$), then the p-value for comparing treatments for the primary endpoint will be reported from a non-parametric ANCOVA model with the response and baseline covariate variables replaced by their ranks.

PROC RANK DATA=ANAL OUT=RANKED TIES=MEAN;

VAR BASE CHG;

RANKS RBASE RCHG;

RUN;

PROC MIXED DATA=RANKED METHOD=TYPE3;

CLASS TRT03PN;

MODEL RCHG = TRT03PN RBASE BMED;

RUN;

An estimate of the median difference between treatments for the primary endpoint will be reported using Hodges and Lehman analysis.

PROC NPAR1WAY HL ALPHA=.05 DATA=ANAL;

CLASS TRT03PN;

VAR CHG;

RUN;

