9.9.1.1. Primary Efficacy Analysis

An analysis of covariance (ANCOVA) model will be used to analyze the primary efficacy endpoint of change in ESS score. The model will include treatment group, randomization stratum, and the efficacy measurement at the end of the Stable Dose Period as fixed effects.

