5.4. Power and Sample Size Considerations

A sample size of 56 subjects randomized per treatment group (total randomized sample size of 112 subjects) will provide 91.8% power to detect a difference of 3.5 points for the change in ESS between JZP-258 and placebo, from the end of the SDP to the end of the DBRW. This study was originally designed to include an optional IA for efficacy; thus, calculations were based on the following: a 2-sample Z test with a group-sequential design including one IA at 60% information fraction using a Lan-Demets alpha spending function that approximates the O'Brien-Fleming boundaries, a common standard deviation (SD) of 5.5 points in the change in ESS for both arms, and a 2-sided significance level of 0.05. Assuming a 20% dropout rate prior to randomization, approximately 140 subjects will be enrolled.

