7.3. Hypotheses Testing

The null and alternative hypotheses for the primary endpoint are:

$$H_0: \mu_{JZP-258} = \mu_{Placebo}$$

$$H_1: \mu_{JZP-258} \neq \mu_{Placebo}$$

Specifically, the null hypothesis states that there is no difference between the mean change in ESS from the end of the SDP to the end of the DBRW between the JZP-258 and placebo treatment groups. The alternative hypothesis states that the mean change in ESS is not equal between JZP-258 and placebo treatment groups.

Subjects who are randomized to continue JZP-258 in the DBRW will be treated as a single group regardless of the dose and regimen of JZP-258 received. Thus, there will be no multiplicity adjustments with respect to multiple doses for hypotheses testing.

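### A normality pre-test on the trial's own residuals can move the primary ESS p-value to a rank test that does not target the powered mean difference, and can cost substantial power if only a minority of placebo subjects relapse

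*SAP*

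**What the plan says.** Protocol 9.9.1.1 gives one primary method: "An analysis of covariance (ANCOVA) model will be used to analyze the primary efficacy endpoint of change in ESS score". It mentions no normality test and no fallback.

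SAP 9.1.1 keeps that ANCOVA as the main analysis, with treatment, baseline medication group and end-of-SDP ESS in the model. It then tests the residuals by Shapiro-Wilk at 0.05 and adds: "If the normality assumption is considered violated, a non-parametric ANCOVA with the covariate and response variables replaced by their ranks" becomes the primary efficacy analysis. The p-value then comes from the rank model, and the effect is described by a Hodges-Lehmann estimate with an asymptotic interval.

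The hypothesis and the sample size are both about means. In SAP 7.3, "the null hypothesis states that there is no difference between the mean change in ESS" between the arms. In SAP 5.4, 56 subjects per arm "will provide 91.8% power to detect a difference of 3.5 points for the change in ESS between JZP-258 and placebo", with "a common standard deviation (SD) of 5.5 points in the change in ESS for both arms, and a 2-sided significance level of 0.05".

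IHSS (SAP 9.2.2) and FOSQ-10 (SAP 9.3.2) are analysed in the same way by reference to 9.1.1, as are the exploratory endpoints. The only sensitivity analysis of the primary endpoint (SAP 9.1.2, baseline observation carried forward) also follows 9.1.1. SAP 7.6 lists three changes from the protocol, and the switch is not among them.

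**The concern.** The observed data decide which hypothesis the confirmatory p-value addresses. If the pre-test rejects, the trial's primary test is no longer a test of equal mean change, although that is the null stated and the effect powered. No section clearly keeps the ANCOVA on means as the test of record after a switch.

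The design makes the question practical. In a randomized withdrawal trial, some placebo subjects may relapse strongly while others hold their response. If the relapsing share is small, the residuals are a skewed mixture. Shapiro-Wilk detects that shape readily, and it is a shape in which ranks discard much of the information in the mean, because a large worsening counts for little more than a moderate one. At stake is power for the primary endpoint, and for the key secondary endpoints that can be tested only if it succeeds.

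**Working it through.** **1. The plan's own figure.** The inputs from SAP 5.4 are 56 per arm, difference 3.5, SD 5.5, two-sided 0.05, and "a 2-sample Z test with a group-sequential design including one IA at 60% information fraction".

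- Standard error = 5.5 × √(2/56) = 1.039, so the standardised difference is 3.5 / 1.039 = 3.367.
- Fixed design: Φ(3.367 − 1.960) = 92.0%.
- Group-sequential design, with the two-sided boundaries 0.0075 and 0.0476 of Protocol 9.9.2, Table 7, at information 0.60: 91.84%, overall alpha 0.04995. This reproduces the stated 91.8%.
- "This SAP confirms that an interim analysis was not performed", so the final test uses the full 0.05 and 92.0% is the relevant benchmark for a test on means.

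**2. Simulating the SAP 9.1.1 rule.** Each simulated trial fits the ANCOVA (treatment, end-of-SDP ESS, stratum), applies Shapiro-Wilk to the residuals, and takes the rank ANCOVA p-value if that test gives p<0.05. There were 10,000 trials per scenario with 56 per arm. End-of-SDP ESS was drawn with mean 6.5 and SD 4, rounded and limited to 0-24, in three strata; these are assumptions.

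A share p of placebo subjects relapses by 3.5/p points, so the mean difference is 3.5. JZP-258 subjects have mean change 0. The within-group SD s is set so that the pooled SD is 5.5: s² = 30.25 − p(1−p)(3.5/p)²/2. For p = 0.25 the relapse is 14 points and s² = 30.25 − 18.375 = 11.875, so s = 3.45. The relapse shares and sizes are assumptions, because the documents give none.

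Paired entries are unbounded change / change rounded and bounded so that ESS stays within 0-24. Bounding reduces the mean difference to about 3.1-3.3.

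| Scenario | s | Switch rate | ANCOVA power | Power under the SAP rule |
|---|---|---|---|---|
| 25% relapse by 14 | 3.45 | 91% / 93% | 92% / 93% | 63.5% / 63% |
| 33% relapse by 10.6 | 4.22 | 16% / 35% | 91% / 93% | 88% / 86% |
| 40% relapse by 8.8 | 4.59 | 6% / 18% | 91% / 92.5% | 90.5% / 90.5% |
| 50% relapse by 7 | 4.91 | 4% / 12% | 91% / 92% | 91% / 91% |
| 67% to 80% relapse | 5.22 to 5.36 | 5% / 12-14% | 90-91% / 90-91% | 90-91% / 90% |
| Normal, shift 3.5, SD 5.5 (unbounded) | 5.5 | 5% | 91% | 91% |
| t with 3 df, SD 5.5 (unbounded) | – | 88% | 91% | 99% |
| t with 4 df, SD 5.5 (unbounded) | – | 71% | 91% | 97% |

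**3. Tighter within-group SD (1.5-2.5), mean difference 3.5.** With 25% relapsing, power under the rule is 62-64%, against 97-99% for ANCOVA. With 33%, the switch rate is 68-97% and power is about 86-87% against 99% or more, a loss of about 13 points. With 40%, the loss is about 3 points.

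**4. Type I error.** When both arms have the same distribution the rule rejects 4.9% of the time, both with normal data and with 25% of each arm relapsing by 14.

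**5. Which null the rank test addresses.** Let 25% of placebo subjects change by +10.5 and 75% by −3.5, so the mean is 0.25 × 10.5 − 0.75 × 3.5 = 0. JZP-258 is centred at 0, and the within-group SD is 2.5. The means are equal. ANCOVA rejects 5.4% of the time and the SAP rule 65%.

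**The case against.** The rule is deterministic and pre-specified, leaves no analyst discretion, and holds type I error when the arms share one distribution. It can also help: with symmetric heavy tails it raises power from 91% to 97-99%. Bounding ESS to 0-24 typically shrinks that gain without removing it. Bounded runs with heavy-tailed errors gave 96.9% to 98.2%, 97.5% to 98.9%, 79.1% to 85.4% (difference about 2.3) and 85.7% to 93.8% (difference about 1.9). The equal-means example requires most placebo subjects to improve on withdrawal, which is implausible here; it shows only that the rank test has a different null. All of this stands, and it limits the point.

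Four stronger readings are tempting, and the documents do not support them.

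- A reader might infer that any partial relapse, being natural to a withdrawal design, will probably trigger the switch and weaken the test. The documents give no relapse share, and at the planning SD a share of 40% or more seldom triggers it.
- A reader might infer that the mean difference disappears from the report after a switch. SAP 9.1.1 promises LS means, their difference and its interval without stating a condition, so it may well still be reported. What is missing is a statement of its status after a switch.
- A reader might infer that the hierarchy breaks if ESS and IHSS end up on different tests. A fixed sequence needs only a valid p-value for each null, and this one already contains a CMH test of a proportion (SAP 9.2.1).
- A reader might treat the omission from SAP 7.6 as concealment. Protocol 9.1 leaves analysis detail to the SAP, and SAP 9.1.1 describes the switch openly. It is a gap in the list of changes.

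**Conclusion.** The concern holds in a limited form. The pre-test can move the primary p-value to a test that does not match the stated null or the powered effect, and this addition to the protocol's ANCOVA is not listed in SAP 7.6. Validity in the usual sense is not at issue.

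The power cost depends on the assumed relapse share. At a mean difference of 3.5 and pooled SD of 5.5 it is about 29 points when a quarter of placebo subjects relapse, about 3-7 points at a third, and about 2 points or less at 40% and above. With tight within-group SD the losses are about 13 points at a third and about 3 at 40%. Normal residuals cost nothing, and heavy tails reverse the sign. These scenarios match the planned pooled SD but not the planned equal SD in each arm, since relapse in a subset widens the placebo arm only. The change is worth making because a large loss is possible under a plausible pattern and the remedy is cheap.

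**What to change.** Delete the Shapiro-Wilk switch from SAP 9.1.1. Keep ANCOVA on change in ESS, with the LS mean difference, 95% CI and p-value, as the primary analysis whatever the residuals look like. Heteroscedasticity-consistent standard errors can be added if wanted, since partial relapse makes the arm variances unequal. Report the rank ANCOVA and the Hodges-Lehmann shift as pre-specified sensitivity analyses. Apply the same to IHSS and FOSQ-10, and align SAP 9.4.4, which carries the parametric or non-parametric choice into the subgroups.

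If the rank model is kept as a sensitivity analysis, correct its example code. It names only treatment in the CLASS statement, so a numerically coded baseline medication group would enter as a linear trend and not as the stated fixed effect. The Hodges-Lehmann code has no covariates, so the report should say that its interval and the rank p-value come from different models.

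The cost is SAP wording only, if done before the unblinding described in SAP 5.6. The downside is some loss of power if residuals turn out heavy-tailed; the rank sensitivity analysis would still show that result.

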9.1.2. Sensitivity Analyses of the Primary Efficacy Endpoint

Sensitivity analysis using Single Imputation: For subjects without post-randomization ESS data, the result from the end of the SDP will be carried forward (i.e. Baseline observation Carried Forward [BOCF] approach) and analyzed as described section 9.1.1.

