9.2.2. Change in IHSS

The next key secondary efficacy endpoint is the change in total IHSS score from the end of the SDP to the end of the DBRW. The IHSS is a 14-item self-reported questionnaire that assesses the severity of IH (Dauvilliers et al 2019). Questions capture symptoms of excessive sleepiness, sleep inertia, and sleep duration. Symptom frequency, intensity, and consequences are rated using a 3- or 4-point Likert scale, providing total scores that range from 0 to 50. Higher scores indicate more severe and frequent symptoms.

The IHSS total score is the sum of the 14 item-scores. Item 14 will be scored as “0” (no problem) for subjects who indicate they do not drive. If four or more item scores are missing at a specific time point, the IHSS total score will be set to missing. If less than four IHSS item scores are missing at a specific time point, then impute each missing item by multiplying the missing item’s maximum response value by the average of the remaining non-missing items proportion of maximum response.

Let Q_i be the score and M_i be the maximum possible score for each of the observed responses for the 14 items $i \in \Psi = \{1, 2, \dots, 14\}$. If the total number of items missing are less than 4 ($N < 4$) and M_j represents the maximum score for the missing item, then the score for each missing item $Q_j, j \in \Omega = \{l_1, l_2, \dots, l_N\}$, will be imputed as

$$Q_j = M_j * \left(\sum_{i \in \Psi} Q_i / M_i \right) / (14 - N) \quad j \in \Omega$$

Note that the maximum possible score can be either 3 or 4 depending on the specific question. The IHSS total score will be then calculated as the sum of the observed and imputed item scores as follows:

$$S = \sum_{i \in \Psi \setminus \Omega} Q_i + \sum_{j \in \Omega} Q_j$$

The change in IHSS total score will be summarized and analyzed similarly to the primary efficacy endpoint (refer to section 9.1.1 for details on the model and SAS code).

Two additional scores will be calculated from the IHSS questionnaire based on the following items:

- Component I is composed of five items focusing on “Night/Inertia” (Questions 1, 2, 3, 4 and 8)
- Component II includes nine items focusing on “Day/Performances” (Questions 5, 6, 7, 9, 10, 11, 12, 13 and 14)

The change in each IHSS Component will be analyzed similarly to the primary efficacy endpoint. Analysis of IHSS Components I and II are considered exploratory.

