Appendix 1: Programming Conventions for Outputs

Outputs will be presented according to the following:

Paper size, orientation, and margins: The size of paper will be Letter. The page orientation will be landscape; Margins should provide at least 1 inch (2.54 centimeters) of white space all around the page, regardless of the paper size.

Fonts: The font type ‘Courier New’ will be used as a default for tables and listings, with a font size of 8. The font color will be black. No **bolding**, underlining, *italics* or subscripting will be permitted.

Super-scripts will be avoided, unless absolutely necessary. Single spacing will be used for all text.

SDTM Terminology: When possible, SDTM controlled terminology (e.g., race) will be used in the tables, listings and figures outputs.

Dates & Times

Depending on data available, dates and times will take the form yyyy-mm-ddThh:mm:ss.

Spelling Format

English US, with the exception of the MedDRA SOCs and PTs for which British English will be used.

Presentation of Treatment Groups

For outputs by Baseline Medication Group, the groups will be presented as follows and in that order:

Group Number	Baseline Medication Group	For Tables, Figures, and Listings
1	Subjects on Xyrem only	Xyrem Only
2	Subjects on Xyrem and an additional stimulant or alerting agent	Xyrem + Stimulant or AA
3	Subjects on a stimulant or alerting agent only	Non Xyrem Stimulant or AA Only
4	Subjects not currently taking	Treatment Naïve

	Xyrem or a stimulant or alerting agent	
--	--	--

For outputs by randomized treatment group, the groups will be presented as follow and in that order:

Randomized Treatment Group	For Tables, Figures, and Listings
JZP-258	JZP-258
Placebo	Placebo

Number of Decimal Places to Be Presented

For descriptive statistics, the same number of decimal places as in the raw data will be presented when reporting minimum and maximum, 1 more decimal place than in the raw data will be presented when reporting mean and median, and 2 more decimal places than in the raw data will be presented when reporting SD. If the raw data has 3 decimals or more, 3 decimals will be presented for mean, SD, median, minimum, and maximum.

For percentages, 1 decimal place will be presented.

For LS means, LS mean differences, SEs, and CIs, 2 more decimal places than in the raw data will be presented. If the raw data has 3 decimals or more, 3 decimals will be presented.

For p-values, 4 decimal places will be presented.

Listings

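### SAP 9.1.1: the example rank-ANCOVA code leaves baseline medication group out of CLASS, so as printed it does not fit the model the text specifies

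*SAP*

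**What the plan says.** SAP 9.1.1 describes the main analysis of change in ESS as an ANCOVA with a fallback. If Shapiro-Wilk rejects normality of the residuals at 0.05, a rank version is used, with "treatment and baseline medication group as fixed effects, and the rank for ESS score at the end of SDP as a covariate". Medication group is therefore a factor, and the ranked end-of-SDP ESS is the only covariate. Protocol 9.9.1.1 likewise lists the randomization stratum among the fixed effects.

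The parametric example code agrees with this: its CLASS statement is "CLASS TRT03PN BMED". In the rank-model step the CLASS statement is only "CLASS TRT03PN", while the model line is still "MODEL RCHG = TRT03PN RBASE BMED".

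The sentence introducing that code says that, when normality is rejected, "the p-value for comparing treatments for the primary endpoint will be reported from a non-parametric ANCOVA model". Other analyses point to the same section. SAP 9.2.2 tells the reader, for IHSS, to "refer to section 9.1.1 for details on the model and SAS code". The BOCF sensitivity analysis in SAP 9.1.2 is to be "analyzed as described section 9.1.1".

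SAP Appendix 1 numbers the medication groups 1 to 4: Xyrem only, Xyrem plus a stimulant or alerting agent, "Non Xyrem Stimulant or AA Only", and treatment naive.

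**The concern.** The text and the code in one section describe different models for what may be the confirmatory p-value. In PROC MIXED, whether BMED enters as a factor depends only on whether it is listed in CLASS. The SAP does not say whether BMED is numeric or character, and with four groups neither type gives the specified model:

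- **Numeric, coded 1 to 4.** BMED becomes one straight-line term. It forces equal steps from group 1 to 2, 2 to 3 and 3 to 4, although the numbers are labels with no order. The step runs without an error, so the mismatch could go unnoticed.
- **Character.** The step stops with an error.

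At stake is whether the reported p-value comes from the pre-specified model, for ESS and for IHSS, the last endpoint in the testing hierarchy. A conflict left in place also invites argument after unblinding about which version was pre-specified.

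**Working it through.** **Inputs from the documents.** SAP 5.4: 112 randomized, 56 per arm; difference 3.5 points; SD of change 5.5; two-sided alpha 0.05; stated power 91.8%. SAP 5.5: four strata, 1:1 randomization stratified by them. The documents give no stratum sizes or stratum effects, so these are assumptions below.

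**The plan's own figure.** The standardized difference is 3.5 / (5.5 × √(2/56)) = 3.5 / 1.039 = 3.367. Fixed-design power is Φ(3.367 − 1.960) = Φ(1.407) = 92.0%. With one look at information fraction 0.6 and O'Brien-Fleming-type spending (final two-sided boundary 0.0476), power is 91.84%. The stated 91.8% is reproduced, and the coding point does not alter it.

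**Degrees of freedom at N = 112, all four groups present.**

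| | Intercept | Treatment | RBASE | BMED | Residual df |
|---|---|---|---|---|---|
| BMED in CLASS | 1 | 1 | 1 | 3 | 112 − 6 = 106 |
| As printed, BMED numeric | 1 | 1 | 1 | 1 | 112 − 4 = 108 |

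**What the slope can miss.** Assume equal strata of 28 and stratum effects of 0, +4, −2, +3 points. Their sum of squares about the mean of 1.25 is 29 − 4 × 1.25² = 22.75. The fitted slope on 1 to 4 is 1.5/5 = 0.3, which explains 0.3 × 1.5 = 0.45, or about 2%. Nearly all of the stratum variation stays in the residual.

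On the unranked scale the residual SD is then √(5.5² + (22.75 − 0.45)/4) = √35.83 = 5.99, against 5.5 with CLASS. Because treatment is balanced within strata, the true variance of the treatment estimate still reflects 5.5. The test therefore behaves as if its critical value were 1.96 × 5.99/5.5 = 2.13:

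- type I error ≈ 2 × (1 − Φ(2.13)) = 3.3%;
- power at 3.5 points ≈ Φ(3.367 − 2.13) = 89%, against 92%.

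So the error runs in the conservative direction.

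**Simulation of the rank model** (2,000 trials per cell, stratified 1:1, SD 5.5 within stratum, effects 0/+4/−2/+3 where present):

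| Stratum shares | Stratum effects | Power at 3.5, printed | Power at 3.5, CLASS | Type I, printed | Type I, CLASS |
|---|---|---|---|---|---|
| 25/25/25/25% | none | 90.4% | 90.6% | 5.4% | 5.5% |
| 4/4/50/42% | none | 89.4% | 89.5% | 6.0% | 5.7% |
| 25/25/25/25% | 0/+4/−2/+3 | 85.4% | 88.9% | 3.1% | 4.3% |
| 4/4/50/42% | 0/+4/−2/+3 | 86.8% | 89.2% | 3.2% | 4.7% |

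A wider set of 72 cells used strata of 28/28/28/28, 6/16/50/40 and 2/4/58/48, with end-of-SDP ESS of mean 6 and SD 4. Each cell was run with the final score either unrestricted or clipped to 0–24. Results:

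- Loss at 3.5 points was about 0 with no or linear (0/1/2/3) stratum effects, and about 1 point with 0/+2/−1/+1.5.
- Loss was larger with 0/+4/−2/+3. A further unclipped run of 4,000 trials per cell gave 3.6, 4.4 and 2.0 points for the three sets of strata, in the order listed.
- At a 2.0-point difference the losses were about 0, 1–2 and 4–8 points respectively.
- Type I error was 2.5–5.8% as printed and 3.8–6.0% with CLASS.
- Shapiro-Wilk rejected in about 4–6% of unclipped trials. In clipped trials it rejected in about 7–19% at 3.5 points, 10–28% at 2.0 and 17–41% at 0.
- Normality was rejected and the verdict also differed in at most 0.45% of trials at 0 and 3.5 points, and at most 1.08% at 2.0 points.

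**The case against.** The strongest reply is that the controlling text is complete and correct, the code is headed as an example, and the parametric block shows the intended CLASS line. A programmer following the text would fit the right model, and with a character BMED no wrong p-value could be produced. Harm needs a numeric BMED with more than two levels, the code run as printed, a Shapiro-Wilk rejection, and stratum effects that are not linear in the group number. All of this stands, and it is why the point is minor.

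The size of the power loss is also open to challenge. The simulations add stratum effects to a within-stratum SD of 5.5, which raises the total SD to about 6.0–6.1. If the total SD is held at the planned 5.5, the printed code keeps 92.0%, 92.6% and 93.4% power for the three sets of strata with 0/+4/−2/+3. The loss relative to CLASS is then about 2–3 points. On that reading the printed code gives up precision that the sample size never counted on, and power stays at about the planned 91.8%. The assumed effects also span 6 points, more than the treatment effect itself, and nothing in the documents supports them. This stands too.

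A numeric BMED pooled to two levels would make the printed code equivalent to the text. SAP 7.1 does describe pooling, but for summaries and for the baseline-medication subgroup analyses. It does not say that pooling applies to the ANCOVA factor.

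None of this removes the mismatch. The code is tied to the primary p-value, IHSS is directed to the code as well as the model, and no other passage corrects the line.

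**Conclusion.** The code is wrong as written and the specified analysis is right. Run as printed with the four groups, the rank step either fits a 1-df slope where the text requires a 3-df factor, or does not run.

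Severity is minor. No bias is expected and the simulations showed no type I inflation. The possible cost is a somewhat conservative test: no loss with no or linear stratum effects, about 1 point with moderate non-linear effects, and about 2 to 4 points with large ones, all at a 3.5-point difference. The estimated chance that normality is rejected and the verdict also changes is about 1% or less. These are simulation estimates rather than bounds. They assume a numeric BMED coded 1 to 4, code run as printed, and stratum sizes and effects that the documents do not give. Only the p-value is exposed: the Hodges-Lehmann estimate and interval come from a separate step that does not use BMED.

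**What to change.** In the rank-model PROC MIXED step of SAP 9.1.1, replace the CLASS statement with the one already used in the parametric step, "CLASS TRT03PN BMED". The code then fits the model in the text, including for the analyses that refer back to 9.1.1.

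The cost is one word in one line of example code, best corrected before unblinding. The alpha level, the 91.8% power and the sample size of 112 do not change.
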